9 DISSEMINATION POLICY

9.1 Dissemination policy

Upon completion of the data collection and data analysis, a Final Study Report will be prepared and will be considered for presentation/publications. Information will be given to the patients on how to ask for a copy of the results. A patient friendly lay summary of the research will be produced and made available to participants if they wish.

9.2 Authorship eligibility guidelines and any intended use of professional writers

Authorship on the final study report will be granted to chief investigator and study supervisor

11. APPENDICES

11.1 Appendix 1- QLQ-C30

11.2 Appendix 2 - QLQ-OES18

11.3 Appendix 3 – Semi-structured interview schedule

APPENDIX 1

ENGLISH

EORTC QLQ-C30 (version 3)

We are interested in some things about you and your health. Please answer all of the questions yourself by circling the number that best applies to you. There are no "right" or "wrong" answers. The information that you provide will remain strictly confidential.

Please fill in your initials:

Your birthdate (Day, Month, Year):

Today's date (Day, Month, Year):

31				

1. Do you have any trouble doing strenuous activities, like carrying a heavy shopping bag or a suitcase?
2. Do you have any trouble taking a long walk?
3. Do you have any trouble taking a short walk outside of the house?
4. Do you need to stay in bed or a chair during the day?
5. Do you need help with eating, dressing, washing yourself or using the toilet?

	Not at All	A Little	Quite a Bit	Very Much
--	------------	----------	-------------	-----------

During the past week:

6. Were you limited in doing either your work or other daily activities?
7. Were you limited in pursuing your hobbies or other leisure time activities?
8. Were you short of breath?
9. Have you had pain?
10. Did you need to rest?
11. Have you had trouble sleeping?
12. Have you felt weak?
13. Have you lacked appetite?
14. Have you felt nauseated?
15. Have you vomited?
16. Have you been constipated?

	Not at All	A Little	Quite a Bit	Very Much
--	------------	----------	-------------	-----------

Please go on to the next page

Functional Outcome Ivor Lewis

During the past week:

During the past week:		Not at All	A Little	Quite a Bit	Very Much
17.	Have you had diarrhea?	1	2	3	4
18.	Were you tired?	1	2	3	4
19.	Did pain interfere with your daily activities?	1	2	3	4
20.	Have you had difficulty in concentrating on things, like reading a newspaper or watching television?	1	2	3	4
21.	Did you feel tense?	1	2	3	4
22.	Did you worry?	1	2	3	4
23.	Did you feel irritable?	1	2	3	4
24.	Did you feel depressed?	1	2	3	4
25.	Have you had difficulty remembering things?	1	2	3	4
26.	Has your physical condition or medical treatment interfered with your family life?	1	2	3	4
27.	Has your physical condition or medical treatment interfered with your social activities?	1	2	3	4
28.	Has your physical condition or medical treatment caused you financial difficulties?	1	2	3	4

For the following questions please circle the number between 1 and 7 that best applies to you

29. How would you rate your overall health during the past week?

1 2 3 4 5 6 7

30. How would you rate your overall quality of life during the past week?

1	2	3	4	5	6	7
Very poor				Excellent		

APPENDIX 2

ENGLISH

**EORTC QLQ – OES18**

Patients sometimes report that they have the following symptoms or problems. Please indicate the extent to which you have experienced these symptoms or problems during the past week. Please answer by circling the number that best applies to you.

During the past week:	Not at all	A little	Quite a bit	Very much
31. Could you eat solid food?	1	2	3	4
32. Could you eat liquidised or soft food?	1	2	3	4
33. Could you drink liquids?	1	2	3	4
34. Have you had trouble with swallowing your saliva?	1	2	3	4
35. Have you choked when swallowing?	1	2	3	4
36. Have you had trouble enjoying your meals?	1	2	3	4
37. Have you felt full up too quickly?	1	2	3	4
38. Have you had trouble with eating?	1	2	3	4
39. Have you had trouble with eating in front of other people?	1	2	3	4
40. Have you had a dry mouth?	1	2	3	4
41. Have you had problems with your sense of taste?	1	2	3	4
42. Have you had trouble with coughing?	1	2	3	4
43. Have you had trouble with talking?	1	2	3	4
44. Have you had acid indigestion or heartburn?	1	2	3	4
45. Have you had trouble with acid or bile coming into your mouth?	1	2	3	4
46. Have you had pain when you eat?	1	2	3	4
47. Have you had pain in your chest?	1	2	3	4
48. Have you had pain in your stomach?	1	2	3	4

APPENDIX 3

SEMI STRUCTURED INTERVIEW SCHEDULE

Introduction, explanation about proceedings and consent

In general, tell me about how your life has been since your operation.

Can you tell me how you feel about oesophageal cancer and the impact on your life so far?

Post operatively, have your symptoms changed with time? Have they got worse, more frequent? Have new symptoms come on, that weren't there to start with? Would you mind telling me more about them?

What is the main changes/adaptation in your daily activity that you have had to make following surgery?

Can you describe any changes to your life that have happened as a consequence of having the surgery E.g. daily routine, social activities, relationships, quality of life.

How is your appetite, eating and drinking compared to before the operation?

Is there anything else that you would like to discuss, relating to your experience of the JEJ feeding tube, your appetite and food intake that you feel is important?

To facilitate open discussion,

Can you tell me more?

Can you expand on that?

Can you explain what you mean?

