Another common functional problem is reflux. Up to 80% of patients present with symptoms related with acid or bilio-pancreatic reflux. (21,22) Oesophagitis has been reported in 38 to 76% of patients (23) and supra-anastomotic Barrett's metaplasia in 8 to 50%. (24,25) Loss of the anti-reflux mechanism and the exposure of gastric tube to the negative intra thoracic pressure increase chances of developing significant reflux post operatively. Patients would usually present with burning sensations in upper chest and neck worsened by lying in prone position especially at night. This subsequently leads to poor sleep and nocturnal cough. (6) Multiple variation in creating the anastomosis has been studied in an attempt to reduce incidence of post operative reflux, including; formation of a neck anastomosis rather than thoracic anastomosis; retrosternal gastroplasty; pyloroplasty; and creation of peri-anastomotic valve. Nevertheless, these different techniques are not used in routine surgical practice with most surgeons preferring to avoid a more complex surgery.

Functional Outcome Ivor Lewis

Significant gastrointestinal symptoms are associated with dumping syndrome which is relatively common consequence of oesophagectomy with a reported prevalence of between 10 to 50%. The pathophysiology of dumping syndrome is complex but includes rapid transit of a hypersomolar bolus into the jejunum leading to splanchnic vasodilatation and systemic hypotension due to relative hypovolemia. The hyperosmolarity also triggers excessive secretion of various peptides which leads to diarrhoea and inhibition of water and sodium absorption. Symptoms include palpitations, nausea, diaphoresis, flushes, diarrhoea and abdominal cramps. Late dumping can also occur with symptoms of trembling, somnolence and concentration disorder. Small group of patients can present with both accelerated and delayed dumping syndrome. (6)

It is recognised that only a small number of patients are asymptomatic in the long term (10,11) and that the occurrence of functional disorders and postoperative complications has an influence on QOL. Previous studies have shown that the lowest level of QOL occurs at approximately four to six weeks postoperatively. (12,13) Almost 50 percent of the patients have at least one functional disorder within the first month following surgery. (14) Most functional recovery takes place during the first two years after surgery with concurrent improvement in QOL.

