Potential participants for part B will be those recruited into EORTC QOL assessment study. At the initial recruitment stage, participants will be asked to indicate on the consent form if they agree to be interviewed. Purposeful sampling will be adopted to ensure appropriate selection of cases. On agreement, consent will be taken prior to interview taking place. It is anticipated that no more than 15 patients will be included.

The interviews will all follow the same semi-structured format. The interview schedule (APPENDIX 3) has been developed and encourages exploration and discussion of the following areas:

- evaluate changes over time, and factors that may impact patients' quality of life the first year after oesophagectomy for cancer
- illuminate patients' experiences of their quality of life and how they handle their new life situation from a long-term perspective after oesophagectomy for cancer

Interviews will be conducted in a private room with estimated duration approximately 90 minutes. Following each interview, the researcher will make field notes including any observations. This will help to inform reflexive reflection. The interview will be digitally recorded and then transcribed verbatim. Each participant will be assigned a false name when the interview transcribed, and the recording will be destroyed when no longer needed for study purposes. Data organisation and retrieval will be managed using the qualitative software package NVivo.

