Qualitative approach of thematic analysis will be used for this study. The conceptual framework of the thematic analysis was mainly built upon the theoretical positions of Braun and Clarke (28). According to them, thematic analysis can be used for 'identifying, analysing, and reporting patterns (themes) within the data and can produce an insightful analysis that answers particular research questions. A theme is something that captures the key idea about the data in relation to the research question and which represents some level of patterned response or meaning within the data set.

Six phase guide provided by Braun and Clarke will be used as a framework in conducting and analysing this part of the study

Step 1: Become familiar with the data

Step 2: Generate initial codes

Step 3: Search for themes

Step 4: Review themes

Step 5: Define themes

Step 6: Write-up

Questions will be semi-structured and adapted on individual basis to cover themes that might emerge out of discussions.

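### The one interview item on how symptoms have changed since surgery prompts for worsening and new symptoms but not for improvement, no change or resolution

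*Protocol*

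**What the plan says.** Appendix 3 of the protocol (Semi-structured interview schedule) contains one item on the course of symptoms after surgery. It opens with "Post operatively, have your symptoms changed with time", follows with "Have they got worse, more frequent" and then "Have new symptoms come on, that weren't there to start with", and ends by inviting the participant to say more.

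Section 5, Part B, states that "The interviews will all follow the same semi-structured format". The first area it lists for the schedule is change over time in the first year, and the second is the patient's experience from a long-term perspective. Section 6, Part B, adds that "Questions will be semi-structured and adapted on individual basis to cover themes that might emerge out of discussions". The third objective in Section 4.1 is to explore how patients see the changes they have been through since the operation, with a focus on quality of life and gastrointestinal symptoms.

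On the expected course, Section 1 (Background) says: "Most functional recovery takes place during the first two years after surgery with concurrent improvement in QOL". Section 7.2.1 repeats this. Section 1 also says that functional disorders are not always detected straight after surgery and can become more troublesome later.

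**The concern.** An item meant to elicit change in either direction should offer both directions or neither. This one begins with neither and then offers one. A participant who hears only worsening, higher frequency and new symptoms as examples may take these to be the changes of interest and leave out symptoms that eased or went away.

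What is at stake is the balance of the themes on symptom course. Part B expects no more than 15 interviewees and describes no repeat interview. Thematic analysis works on what was said, so an account of recovery that was not elicited cannot be supplied at the coding stage.

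**Working it through.** No arithmetic applies beyond a count, and the plan gives no figure to reproduce. The check is a reading of every question in Appendix 3 against the aims and the expected course stated elsewhere in the protocol.

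**Step 1: the symptom-change item.**

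| Part of the item | Direction named |
|---|---|
| Opening question on change with time | none |
| Worse, more frequent | deterioration |
| New symptoms | deterioration |
| Invitation to say more | none |

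Directional follow-ups: 2. Towards deterioration: 2 of 2. Towards improvement, resolution or stability: 0 of 2.

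**Step 2: the rest of the schedule.** Appendix 3 has seven main questions, counting the symptom-change item as one. The other six name no direction. Examples are "In general, tell me about how your life has been since your operation" and "How is your appetite, eating and drinking compared to before the operation". One of the six asks about changes and adaptation in daily activity. The three general prompts at the end only ask the participant to say more, expand or explain. So 1 of 7 main questions carries one-sided prompts.

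**Step 3: whether another question covers the same ground.** The eating question compares the present with the time before surgery, so it does not trace the course after surgery. The general questions leave room to mention improvement in symptoms but do not ask about it. The symptom-change item is the only one directed at the postoperative symptom course.

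**Step 4: the aim and the expected course.** Section 4.1 and Section 5, Part B, ask about change without giving it a direction. Sections 1 and 7.2.1 expect functional recovery and better quality of life over the first two years. Section 1 also puts the lowest quality of life at about four to six weeks after surgery. Interviewees come from Part A, so they are at least 12 months from surgery and patients with disease recurrence are excluded (Section 7.1). Recovery is therefore a course that many of them could be expected to describe. Section 1 also allows for later worsening. With both courses described in the protocol, the item prompts for one.

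**The case against.** The strongest reply is that the one-sided wording is both justified and harmless.

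- *Justified.* Section 1 expects some disorders to become more troublesome, Section 2 speaks of lasting gastrointestinal consequences, and Section 3 aims to find out whether patients remain compromised in the long term. This stands as a reason to ask about worsening and late-onset symptoms. It is no reason to leave out improvement. Nor is Part B confined to the period after recovery, because the first area listed for the schedule is the first year.
- *Harmless, because the interviewer can adapt.* Section 6 does allow this, and an interviewer could ask about improvement without any amendment. That stands, and it limits the concern. But the adaptation described is for themes that emerge in discussion. It does not remove the scripted prompts or ensure that the missing one is asked.
- *Harmless, because the opening question is neutral.* A participant can report improvement before either follow-up is put. This also stands in part. The examples that follow still signal which kind of change is wanted.

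A reader might go further and infer that the probes are fixed, that every interviewee receives the one-sided prompt, and that Part B as a whole is tilted towards deterioration. The protocol does not support this. A shared semi-structured format is not verbatim administration, Section 6 permits adaptation, and the other six main questions and the closing prompts are neutral. Nor can it be inferred that accounts of adaptation will be lost, since a separate question asks for them.

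**Conclusion.** The point holds as a minor wording defect in one item of Appendix 3. Both of its directional follow-ups point to deterioration, although Part B is meant to explore change and the protocol describes recovery as well as worsening. The item may lead participants towards accounts of decline. That rests on the general assumption that one-sided examples influence answers, and on the scripted prompts being used broadly as written.

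The size of any shift in the themes cannot be computed from the document. Part B is planned as a thematic analysis, not as an estimate of the proportion improved or worsened, so no numerical result is at risk. Part A is unaffected.

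**What to change.** Keep the opening question and the prompts on worsening and new symptoms, and pair each with its counterpart. For example: *Have they got better, stayed the same or got worse? Have they become more or less frequent? Have any gone away, or have new ones come on?* The invitation to say more can stay as it is.

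The cost is a change to about three lines of Appendix 3 and almost no extra interview time. The questionnaires, the sample and the analysis are unchanged, and the information on worsening is still collected.

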3 THEORETICAL FRAMEWORK

This study focuses on the prevalence of functional complications and their impact on QOL in patients who underwent an Ivor Lewis Oesophagectomy.

This study will assess the prevalence of gastrointestinal symptoms and QOL from beyond the first year following surgery. The aim is to determine whether gastrointestinal side effects and QOL are compromised in the long-term.

This study will also explore in details, the impact of surgery on their quality of life and gastro intestinal symptoms that patients has experienced post operatively.

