4.1 Objectives

The purpose of this study is

- To evaluate mid to long term HRQL in patients that underwent Ivor Lewis Oesophagectomy with gastric pull-up
- To identify clinical factors influencing quality of life post operatively.
- To explore patients perspective on changes that they have experienced post operatively focusing on quality of life and gastro intestinal symptoms.

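### The closing interview question presupposes a feeding tube mentioned nowhere else in the protocol and narrows the only open closing prompt to food intake, which has already been asked about

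*Protocol*

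**What the plan says.** Section 4.1 gives the qualitative objective as patients' own view of the changes since surgery, "focusing on quality of life and gastro intestinal symptoms". Section 3 describes the exploratory part in similar terms, as "the impact of surgery on their quality of life and gastro intestinal symptoms".

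Section 5, Part B, lists two areas that the interview schedule is meant to open up. The first is to "evaluate changes over time, and factors that may impact patients' quality of life the first year after oesophagectomy for cancer". The second is to "illuminate patients' experiences of their quality of life and how they handle their new life situation from a long-term perspective after oesophagectomy for cancer". The same section fixes the conduct of the interviews: "The interviews will all follow the same semi-structured format". Sections 5 and 7.2.1 expect no more than 15 participants.

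Appendix 3 contains seven main questions followed by three generic probes. The sixth question asks: "How is your appetite, eating and drinking compared to before the operation". The seventh and last asks whether the participant has more to raise, but only on matters "relating to your experience of the JEJ feeding tube, your appetite and food intake".

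**The concern.** A closing question in a semi-structured interview lets participants raise what the schedule did not foresee. Here it is tied to three topics, and the first is a feeding tube that the rest of the protocol does not mention. The wording takes for granted that the interviewee had one. A participant who had no tube is asked about something that did not happen. A participant whose main difficulty is, say, reflux, isolation or adjusting to a changed life is directed at the end towards eating.

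What is at stake is the fit between the instrument and the stated aim of Part B. The material for the thematic analysis comes from these interviews, so a prompt that points to one topic can tilt the late part of each interview towards it.

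**Working it through.** No arithmetic applies beyond counting. The check compares the closing question with the aims it serves and with the other questions in the schedule.

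**1. Is the feeding tube grounded elsewhere?** I read 'JEJ' as jejunal; the protocol does not expand it. The tube is absent from:

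- the background (Section 1), rationale (Section 2) and theoretical framework (Section 3);
- the aims and objectives (Sections 4 and 4.1);
- the discussion areas for Part B (Section 5);
- the eligibility criteria (Section 7.1).

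The jejunum is named once, in Section 1, to explain the mechanism of dumping. Section 6 summarises the data proforma as demographics, staging, treatment type and postoperative complications. A tube is not listed, but the proforma itself is not shown, so its absence there cannot be confirmed. Nothing states how many patients had a tube.

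**2. Are the three topics within the aim, and are they new?**

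| Topic in the closing question | Within the aims of Part B? | Already asked? |
|---|---|---|
| Feeding tube | No stated aim covers it | No |
| Appetite | Yes, under gastrointestinal symptoms and quality of life | Yes, question 6 |
| Food intake | Yes, same reason | Largely, question 6 |

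One topic of three has no basis in the protocol. The other two are in scope but largely repeat the preceding question.

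**3. What do the other six questions cover?**

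- Question 1 is an unrestricted opening about life since the operation.
- Question 2 asks about feelings towards the cancer and its impact.
- Question 3 asks whether symptoms have changed, worsened or newly appeared, and invites detail.
- Question 4 asks about adaptations in daily activity.
- Question 5 asks about changes in life, with routine, social activities, relationships and quality of life as examples.
- Question 6 asks about appetite, eating and drinking.

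The main areas of Part B therefore each have a question. What is missing is a final invitation of the same breadth. The generic probes after question 7 only ask the participant to expand on what has been said; they open no new topic.

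**4. To whom does the question go?** Section 5 prescribes one format for all interviews, so by default the question is put to every participant. Section 6, Part B, lets questions be adapted to the individual to follow themes that emerge. An interviewer may therefore depart from the wording, but the written default remains.

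**5. Size.** The issue affects 1 of 7 main questions, in at most 15 interviews.

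**The case against.** The best case for leaving the question alone has four parts.

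First, eating is central to life after this operation. Section 1 describes early satiety, discomfort after meals and advice to eat small, frequent meals, so appetite and intake are on topic. This stands. A reader might infer that the whole closing question lies outside Part B, but the documents support that only for the tube.

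Second, a reader might infer that themes such as reflux, dumping, swallowing or social life will be lost. The documents do not show this. Social activities and relationships are named in question 5, any symptom can be raised under question 3, and the opening question is unrestricted. This also stands, and limits the consequence to a reduced opportunity.

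Third, Section 6 allows adaptation, so a sensible interviewer would skip the tube or widen the prompt. This weakens the concern without removing it. The clause is there to follow emerging themes. It neither explains why the tube is in the schedule nor makes the written prompt any broader.

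Fourth, a reader might fault the schedule because it names none of the functional disorders listed in the background. That does not follow. Leaving symptoms unnamed is a legitimate, non-leading choice in exploratory interviews, and Part B participants come from Part A, where the OES18 already asks about swallowing, early fullness, heartburn and acid or bile reflux.

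**Conclusion.** The point holds as a minor wording defect. The only open closing prompt in the schedule presupposes a feeding tube that the protocol mentions nowhere else, and otherwise returns to topics just covered. It therefore gives no last invitation to raise wider quality-of-life, coping or other gastrointestinal experiences, which are what Part B sets out to explore.

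The size is small: one sentence, up to 15 interviews, and no effect on the questionnaires, regression analyses or any figure in Part A. The conclusion assumes that interviewers use the schedule broadly as written, and that the protocol as read contains every reference to a feeding tube apart from the proforma, which is not shown. It does not require that any participant actually lacked a tube; the documents are silent on that.

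A reader might also suppose that the wording was taken over from a different study. That is possible, but nothing in the protocol shows it, and the point does not depend on it.

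**What to change.** Reword the last question of Appendix 3 as an unrestricted closing prompt, for example: *Is there anything else about your quality of life or your symptoms since surgery that you feel is important?*

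Then either delete the reference to the feeding tube, or make it a conditional question asked only of participants who had one. If the investigators do want to study experience of the tube, it should also be stated as an aim in Section 4.1 and listed among the discussion areas in Section 5.

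Prompts naming individual symptoms are optional and not part of this fix. The cost is one sentence in an appendix and negligible interview time.
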